**3. Abstract:**

Aspiration pneumonia (APn) occurs at a disproportionately high rate in patients with Parkinson's disease (PD) versus healthy age-matched older adults. This study aims to determine the underlying causative factors that contribute to airway protection deficits in PD in order to reduce the incidence of aspiration-related illness in these patients. Previous studies suggest that PD patients present with deficits in airway somatosensation and sensory processing and filtering. However, it remains unknown whether these changes are related to observable motor deficits of swallowing or cough in people with PD. As such, this study aims to 1) better understand the relationships between blunted airway somatosensation, reflex cough sensitivity and effectiveness, and swallowing function in people with PD, 2) determine whether measures of discriminative and affective processing of general airway sensation is/are associated with deficits in reflex cough and swallowing function, as well as 3) determine whether over-filtering of airway stimuli is associated with swallowing or cough deficits.

**4. Background:**

***Airway somatosensation in people with PD***

PD is a progressive neurologic condition that is associated with deficits in both swallowing and cough function, as well as high rates of aspiration pneumonia (APn) (1, 2). Yamanda and colleagues have shown that people with a history of APn demonstrated significantly reduced sensitivity to airway irritants, quantified as a blunted urge-to-cough (UtC) (3). The UtC is a respiratory sensation that precedes a cough bout (4, 5). The UtC is blunted in people with PD as compared with age-matched controls, and even further blunted in people with PD and concomitant dysphagia (6, 7). Our preliminary data strongly suggest that general airway somatosensation is also blunted in people with PD with and without concomitant dysphagia. We hypothesize that blunted airway somatosensation contributes to the development of swallowing and cough deficits in people with PD. The objective of this aim is to determine the relationships between blunted airway somatosensation, reflex cough sensitivity and effectiveness, and swallowing function in people with PD. Based on our preliminary studies, we predict that blunted airway somatosensation will appear earlier (years 0 – 5 post-diagnosis) in the disease process than either cough or swallowing dysfunction, and that by 6-10 years post-

diagnosis, blunted respiratory somatosensation will correlate with reduced reflexive cough sensitivity and effectiveness, and decline in swallow function and safety (Figure 1). We will determine airway somatosensitivity using resistive inspiratory loads (8). We will perform fluoroscopic studies to evaluate swallowing function, and reflex cough testing using capsaicin to determine sensitivity and effectiveness. We will perform these tests in people across a range of disease durations. The rationale is that by determining the general respiratory sensitivity, reflex cough sensitivity to an airway irritant (capsaicin), as well as swallowing and cough effectiveness, we will be able to identify whether the onset of swallowing and/or cough deficits occur after reduced respiratory somatosensation. These data will provide support to our hypothesis that reduced respiratory somatosensation underlies observable motor deficits in swallowing and cough function, as well as reduced reflex cough sensitivity. This will significantly advance our understanding of the perceptual sensory components of airway protective deficits in PD, and provide much needed information regarding why airway protection deficits develop. Such outcomes are critically important to advancing the management of patients with PD and other neurodegenerative diseases.

[figure not shown]

Figure 1. Hypothesized relationship between airway protective behaviors and airway somatosensation with Parkinson's disease duration. PAS is penetration-aspiration score; dtLVC\_H1 is duration from initial hyoid burst (H1) to laryngeal vestibule closure (LVC), UtC is urge to cough.

with PD exhibit deficits in multiple sensory modalities, including proprioception, mechanosensation and olfaction (9, 10, 11). There is a breadth of information regarding somatosensory deficits associated with decline in motor functions such as posture and gait, and much of the literature supports the hypothesis that there is a sensory origin to PD motor symptoms (12). Specific sensory deficits within the upper airway include significantly higher laryngeal somatosensory detection thresholds compared to healthy controls (13), and blunted perception of the urge-to-cough (UtC) to cough-inducing airway irritants (1, 6, 14, 15). These sensory abnormalities occur in conjunction with decreased swallowing safety and cough effectiveness (1, 6, 13). Despite this evidence that changes in upper airway sensation accompany motor deficits, the evaluation and management of airway protection in PD and other neurologic diseases continues to focus solely on observable motor deficits of swallowing.

Changes to brainstem areas involved in swallowing and cough generation are affected at the earliest points in PD (16). While severe dysphagia is typically not seen until later stages of the

Previous studies have shown that multiple airway protective behaviors are impacted in people with PD, most notably, functional decline to the mechanisms of swallowing and cough. The consequence of concurrent swallowing and cough dysfunction is uncompensated airway compromise (silent aspiration), indicative of significant sensory deficits whereby a reflexive cough response is not produced in response to aspirate material in the larynx or airway. People

disease, there are subtle changes that may occur to the pressures generated in the oropharynx during swallowing even in the early and mid-stages (Hoehn & Yahr (H&Y) 1 – 3) (17). Hammer and colleagues (2013) studied 18 patients with PD (mean disease duration: 6 years), and found a moderate correlation ( $r = 0.40$ ,  $p = 0.02$ ) between laryngeal somatosensory thresholds and disease severity. Interestingly, their results did not show deficits of swallowing safety in the PD group even though the PD group had significantly higher laryngeal somatosensory thresholds compared with age matched controls. These researchers suggested that “sensory abnormalities may precede penetration and aspiration deficits in the clinical progression of PD” (Hammer et al., 2013; page 4) (13), which is a hypothesis that is also supported by our preliminary studies.

### Preliminary Studies:

[figure not shown]

Figure 2. Significant differences (\* indicates  $p < .010$ ) between healthy controls (HC) and PD groups according to swallowing safety (PA scores; panel A) and disease severity (Hoehn & Yahr scale; panel B).

of various intensities. Our study compared 14 patients with PD to 13 age and sex matched healthy adults (HCs). The results show that people

with PD exhibit blunted magnitude estimation of inspiratory resistive loads as compared with the control group regardless of whether they exhibit measurable decline in swallowing safety, or of disease severity (Figure 2 panels A and B). These data indicate general respiratory sensation is blunted even when dysphagia is not present, and in the early stages of the disease, thus lending preliminary support to the hypothesis that blunted respiratory somatosensation precedes the onset of swallowing deficits in PD.

*Reflex cough sensitivity is blunted in later PD compared to earlier PD and age-matched controls:* In an ongoing study we are measuring sensitivity to the airway irritant capsaicin by examining the perceived UtC. To date, participants include 76 men and women with PD, ranging from 1 to 23 years post-diagnosis and 51 age-matched control participants. Our interim analysis show that participants within 10 years of diagnosis (Figure 3, PD 1-4 and PD 5-9 groups) do not exhibit a significant difference in the UtC sensitivity as compared to the control group, however the PD 10+ group does exhibit a significantly blunted UtC sensitivity compared to controls (Figure 3).

*General respiratory sensation is blunted in PD, independent of disease severity or swallowing safety:* In order to understand whether people with PD experience blunted respiratory somatosensation we conducted a preliminary study to examine the perception and magnitude estimated of inspiratory loads

[figure not shown]

Figure 3. Urge to cough (UtC) sensitivity slope comparison between healthy controls (HC), and PD duration groups. PD1-4 is 1-4 years post PD diagnosis; PD5-9 is 5-9 years post PD diagnosis; PD 10+ is more than 10 years post PD diagnosis. \* is significantly different at  $p < .001$ .

### Airway sensory processing in people with PD

Central neural processing of sensory stimuli is critical for generating appropriate motor plans, and this sensorimotor relationship is disrupted in PD, resulting in many of the hallmark motor symptoms (9-11). Sensory processing involves both discriminative and affective processing components, and each is critical for generating an appropriate motor response. Discriminative processing refers to the ability to detect and gauge the intensity or magnitude of a stimulus, whereas affective processing refers to determination of stimulus characteristics, such as pleasantness or unpleasantness (4, 18). As well, sensory stimuli may be gated, or filtered, out from connecting to the sensory cortex, and this process is normal and expected for many somatosensory modalities to prevent an over abundance of redundant sensory stimuli (19, 20). Our preliminary data suggest that there are changes in both discriminative and affective processing and filtering of airwaysensation in people with PD as compared to an age- and sex-matched control group (21), however to date it is unknown whether these deficits are related to observable motor deficits of swallowing or cough. The objective of this aim is to determine whether measures of discriminative and affective processing of general airway sensation is/are associated with deficits in reflex cough and swallowing function. Further we aim to determine whether over-filtering of airway stimuli is associated with swallowing or cough deficits. Based on preliminary data we expect that people with PD will exhibit reduced discriminative processing components of airway stimuli. With disease progression, measures of affective processing components will decline and this will directly correlate with diminished reflex cough sensitivity and swallowing function. In order to achieve this objective, we will measure swallowing and cough function, reflex cough sensitivity, and the event-related sensory evoked potential (SEP) to an airway stimulus. We will compare the latency and amplitude of the SEP waveform component peaks to swallowing safety and physiology, and cough effectiveness and sensitivity, in people with PD across a range of disease durations. The rationale is that by determining the relationship between discriminative and affective processing of airway sensation and airway protective behaviors (swallowing and cough) we will better understand what type of sensory deficits are impacting airway protective function.

Although both swallowing and cough clearly have motor components, they are typically not considered to be classic *motor* features of PD, which traditionally includes akinesia, rigidity, and/or tremor of upper and lower extremities. While precise etiology of swallowing and cough deficits in PD remains unknown, a recent study by the Arizona Parkinson's Disease Consortium showed inclusion of alphasynuclein protein in the sensory nerve terminals of the upper airway in 10 PD patients, post-mortem, and that there was a significant association between the amount of

this protein and the presence of dysphagia (22). Schindlbeck et al., investigated somatosensory symptoms in de novo PD patients, and found that although somatosensory symptoms were present in 67% of study participants, there was not neurographic evidence of peripheral nerve damage, strongly indicating that in the early phase of the disease sensory changes are likely *not due to peripheral sensory neuropathy* (23).

Figure 6. Small amounts of penetrant and aspirate material in 2 PD patients.

The neural mechanisms mediating swallowing and cough include a brainstem-mediated pathway as well as a supramedullary pathway (24). Studies have identified activity in multiple cortical areas during swallowing, voluntary cough and reflex cough to capsaicin (e.g., (19, 20, 25). This suggests that in cases where the intensity of a stimulus is insufficient to trigger the brainstem-mediated responses, the accurate perception of respiratory sensations is critically important for the generation of airway protective behaviors. When people with PD experience aspiration, it is typically small amounts of aspirate material that enter the larynx (Figure 6), and the strength of this stimulus is not necessarily adequate to trigger the brainstem-mediated reflex cough response. Therefore, the supra-medullary sensory processing of the airway stimulus is requisite to producing a cough response to eject the aspirate material. Experimentally, cough-inducing stimuli, such as low concentrations of capsaicin, can be used to study the cough response to varying intensities of the stimulus (i.e., those strong stimuli that would presumably activate the brainstem-mediated pathway) and those weak stimuli that likely depend on supra-medullary sensory process to modulate the cough response.

The sensory evoked potential (SEP) is a neural correlate of sensory perception that can be elicited across multiple sensory modalities, for example audition (26) somatosensation (27). For the airway, the SEP can be produced by a mechanical stimulus such as an inspiratory occlusion (28, 29), which is similar to applying the inspiratory loads in terms of serving as a general respiratory

stimulus. The resulting waveform consists of multiple component peaks (Figure 7) that reflect both discriminative and affective sensory processing (30, 31). Specifically, the early peak 'P1' is related to discriminative processing, the 'N1' is related to both discriminative and affective processing, and the later P2, and N2 peaks are related to higher order cognitive processing (32). This technique can also be used to examine sensory filtering, or gating, which is defined as the brain's ability to filter redundant sensory information (28, 32).

[figure not shown]

Figure 7. Airway sensory evoked potential peaks including P1, N1, P2, and N2 from a PD participant. The red and blue areas on the right indicate the locations of electrodes recorded the peaks (Pitts et al., 2016).

**Preliminary studies: Reduced**

|    | P1          |            | N1          |         | P2          |         | N2          |            |
|----|-------------|------------|-------------|---------|-------------|---------|-------------|------------|
|    | Mean (SD)   | P-value    | Mean (SD)   | P-value | Mean (SD)   | P-value | Mean (SD)   | P-value    |
| PD | 0.59 (0.41) | .05 | 0.70 (0.55) | 1.0     | 0.38 (0.35) | 0.69    | 0.27 (0.24) | .02 |
|    | 1.26 (0.91) |            | 0.62 (0.31) |         | 0.34 (0.30) |         | 0.88 (0.68) |            |

Table 4. Means and standard deviations (SD) for the airway SEP (Pitts et al., 2016)

*discriminative and affective processing of airway mechanical stimuli in PD:* We have recently reported the results of our study investigating the processing of an air-puff stimulus to the posterior pharyngeal wall in people with PD. Participants were 13 people with PD, and 7 age- and sex-matched healthy older adults (controls). In both the PD and control participants we were able to successfully record SEP component peaks (Figure 7). People with PD exhibit changes to

both P1 (discriminative) and N2 (affective) peaks as compared to healthy older adults (Table 4). Specifically, people with PD over-filter the P1 and N2 peaks, indicating that there is sensory information that is prohibited from reaching the level of conscious perception and processing. A limitation of this study was that the apparatus for delivering the air puff stimulus was uncomfortable for most participants, and this may have increased attention to the stimulus, which is known to modulate the N1, P2 and N2 peaks (33). Nonetheless, this preliminary study lends support our hypothesis that discriminative and affective processing and stimulus filtering are affected in PD, however it remains unknown whether/how attention affected these results, or whether they relate to changes in the airway protective functions of cough and/or swallowing.

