***SEP Procedures:***

Participants will be asked to refrain from strenuous physical activity, large meals and caffeine for at least four hours prior to participating. The participant will be seated in a private, sound/electrical shielded experimental room, with his or her back, neck and head comfortably supported. The participant will be monitored with a video camera. The electroencephalogram (EEG) will be collected using a 64-channel Electrical Geodesics Inc. (EGI; Eugene, Oregon, USA) net and amplifier system (amplification 20 K, nominal bandpass 0.10–100 Hz). Netstation software will be used for continuous recording of EEG data.

The 64-channel EGI electrode net will be placed on the head of the participant. Each participant will be instructed to breathe normally through a mouthpiece connected to a non-rebreathing valve. The inspiratory port will be connected to an airflow sensing pneumotachograph and inspiratory occlusion valve that obstructs the inspiratory airflow. Airflow, mouth and occlusion valve pressures will be sensed with differential pressure transducers and signal conditioners. Paired, identical inspiratory occlusions will be presented by silently inflating the occlusion valve approximately 50ms after the onset of inspiration, and will last for 150 ms. Each occlusion pair will be separated by a 500 ms interstimulus interval. The occluded breaths will be separated by at least 2 unoccluded breaths. The total time required for the presentation of the occlusions will be 700ms after the onset of inspiration, which is within the normal 1.5 second inspiratory duration. Up to 100 occlusion pairs will be delivered in each experimental trial. The latency from stimulus delivery and amplitude for the P1, N1, P2 and N2 peaks will be recorded from both the first (S1) and second (S2) occlusion.

***Attend/ignore conditions:*** In order to understand and account for the effect of attention to the stimulus on the latency, amplitude, and gating of the airway SEP peaks, we will perform the SEP procedure under 2 conditions: attend and ignore. For the attend condition, participants will be instructed to pay attention to their breathing and press a button one time whenever they feel an obstructed breath. In the ignore trial, the subject will not be given any instructions to pay attention to their breathing, and will be asked to watch a series of neutral affective pictures (IAPS; (58)) and ignore their breathing.

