***SEP outcome measures:*** *a. SEP peaks:* The latency and amplitude of the SEP P1 and N2 peaks under the attend and ignore conditions are the primary outcome variables. Secondary outcome measures include the latency and amplitude of the other component peaks, including N1 and P2 peaks. *b. SEP Gating:* The ratio of the amplitude the peaks generated by the first and second paired occlusions will be calculated for each peak, within the attend and ignore conditions. The primary outcome variable will be the ratio of S2/S1 for the P1 and N2 peaks, and the S2/S1 ratio for N1 and P2 peaks will serve as secondary outcome variables.

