## **Statistical Analysis**

**Aim 1:** A multiple regression analysis will be conducted with the slope magnitude estimation as the outcome and disease duration, age, and sex as the independent variables in addition to their mutual interaction terms. Model selection technique will be adopted to select the optimal parsimonial model deemed for the data. We will also perform subgroup analysis to

compare the slope magnitude estimation between PD patients with PAS (penetration-aspiration scale) no more than 2 and PD patients with PAS greater than 2 by adjusting confounding factors of age, gender and BMI, etc. to demonstrate that reduced slope of magnitude estimation is present in PD patients regardless of PAS status. We will include other swallow and cough outcome variables in this model to determine relationships between dependent variables.

**Aims 2 and 3:** We will first fit a multiple regression model with P1 and N2 peak amplitude and gating ratios as the dependent variable and condition (1 = attend and 2 = ignore) as independent variables by controlling confounding variables including age, gender, BMI, etc. In order to determine the relationship between P1 and N2 peaks and swallow and cough function, we will fit a second multiple regression model with P1 and N2 (amplitude and gating ratio), cough and swallow outcomes as the dependent variables and disease duration as the primary independent variable by controlling confounding variables including age, gender, BMI, etc. Also, model selection technique will be adopted to select the optimal model. Besides the primary outcomes of P1 and N2 peaks, other secondary outcomes such as N1 and P2 amplitudes and gating ratios will be analyzed.

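### The attend/ignore analysis estimates only an average attention effect; it does not test whether that effect differs between PD and controls or with disease duration

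*Combined protocol and SAP*

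**What the plan says.** All references are to the combined protocol and SAP.

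- **Background, preliminary SEP study.** The pilot compared 13 people with PD and 7 controls, and reported over-filtering of P1 and N2 in PD. Its stated limitation is that the air-puff apparatus was uncomfortable and "this may have increased attention to the stimulus, which is known to modulate the N1, P2 and N2 peaks". It concludes that "it remains unknown whether/how attention affected these results".
- **SEP Procedures, attend/ignore conditions.** Each participant is tested twice, so as to "understand and account for the effect of attention to the stimulus" on latency, amplitude and gating. In the attend run, participants "press a button one time whenever they feel an obstructed breath".
- **SEP outcome measures.** "The latency and amplitude of the SEP P1 and N2 peaks under the attend and ignore conditions are the primary outcome variables". The S2/S1 gating ratio is also formed within each condition, with P1 and N2 primary.
- **Statistical Analysis, Aims 2 and 3.** A first regression of P1 and N2 amplitude and gating has "condition (1 = attend and 2 = ignore) as independent variables", adjusted for age, gender, BMI and similar. A second, which also covers the cough and swallow outcomes, has "disease duration as the primary independent variable by controlling confounding variables including age, gender, BMI, etc". Neither contains a PD/control term, an interaction or a participant effect. The text does not say which condition's data enter the second regression.
- **Contrast within the plan.** Interactions are named for Aim 1, and a participant random effect for Aim 4. Neither is named for Aims 2 and 3.

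**The concern.** The question the pilot left open is whether a PD-control difference in the SEP reflects attention rather than airway processing. With two conditions per person, the quantity that bears on it is the change in the attend-ignore difference between PD and controls or, within PD, across disease duration. That is an interaction, and neither planned regression contains it.

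The first regression shows whether attention shifts the peaks on average, which is a manipulation check. The second shows whether the peaks change with duration, without separating the conditions. Hypothesis 2 predicts that affective components decline with progression, and the pilot text labels N2 affective. A fall in N2 with duration could be taken as support without any estimate of how much of it depends on attending. N2 is both a primary peak and one the protocol names as modulated by attention. P1 is primary but is not on that list.

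**Working it through.** **Plan's own figure.** There is none to reproduce. Protocol 1 aims for 30 participants per group and gives no power, alpha or effect size.

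**What each model can estimate.** Let x be standardised disease duration, s the slope of the sensory response on x, and a the slope of the attention contribution on x, present only in the attend run.

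- Duration slope in ignore: s
- Duration slope in attend: s + a
- Duration slope on the two-condition average: s + a/2
- Condition-by-duration interaction: a

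Two different causes can give the same average slope:

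- Attention only (s = 0, a = -0.5): 0 + (-0.5)/2 = -0.25
- Sensory only (s = -0.25, a = 0): -0.25 + 0 = -0.25

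The interaction is -0.5 in the first case and 0 in the second.

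**Simulation.** Assumptions: 30 PD participants, unit variance in each condition, within-person correlation 0.5, mean attend-ignore difference 0.5, no covariates, two-sided 0.05, 4,000 runs. Entries are the share of runs significant.

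| Quantity tested | Attention only (a = -0.5) | Sensory only (s = -0.25) |
|---|---|---|
| Average attend-ignore difference (first regression, tested as paired) | 65% | 76% |
| Duration, two-condition average | 31% | 31% |
| Duration, attend only | 74% | 25% |
| Duration, ignore only | 5% | 25% |
| Condition x duration | 73% | 5% |

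A normal approximation agrees roughly. For the average, the residual variance is 0.5 + 0.5/2 = 0.75, the standard error is √(0.75/30) = 0.158, and 0.25/0.158 = 1.58. For the interaction, the variance is 2(1 - 0.5) = 1, the standard error is √(1/30) = 0.183, and 0.5/0.183 = 2.74.

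**Range.**
- For a from -0.3 to -0.8 with s = 0, the duration test is significant in 15% to 66% of runs on the average and 34% to 98% in attend alone; the interaction is detected in 35% to 97%.
- For correlation 0.3 to 0.7 at a = -0.5, the figures are 28% to 36% for the average and 58% to 90% for the interaction.
- A second set-up used sensory SD 1, attention-gain SD 0.7 to 1.0, noise variance 0.3, and a gain-duration correlation of -0.3 to -0.7. It gave 13% to 75% in attend, 8% to 36% on the average, about 5% in ignore, and 18% to 90% for the attend-minus-ignore contrast.

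**A main effect is not enough.** Because every person has both conditions, adding condition to the duration model as a main effect leaves the duration coefficient unchanged (-0.156 either way in a worked data set).

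**No participant effect.** Suppose both conditions are stacked as independent rows, with unit variance and correlation 0.5.
- Duration slope: the nominal variance is 1/60 and the true variance is 0.75/30 = 1/40, so the standard error is understated by a factor √(40/60) = 0.82.
- Condition difference: the nominal variance is 2/30 and the true variance is 1/30, so the standard error is overstated by √2 = 1.41.

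**If ignoring is incomplete.** When 30% to 50% of the attention effect persists in the ignore run (second set-up), the ignore-condition duration test is falsely significant in about 6% to 32% of runs, and detection by the contrast falls to about 10% to 78%.

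**The case against.** The strongest reply is that the SEP outcomes are defined separately for attend and ignore. The second regression may well be fitted to each, which would supply an ignore-condition duration estimate. That is a fair reading, and the condition-specific estimates would be useful. It does not close the gap: finding an effect in one condition and not in the other is not a test that the two differ, and no PD/control comparison is planned in either condition.

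A reader might infer more: that the plan will report loss of attention with advancing disease as loss of airway sensory processing. The documents do not support that. The pilot's question was PD versus control, and the worry was discomfort raising attention. Nothing says that attention declines with duration; the simulations assume it. The move from air puff to inspiratory occlusion also partly deals with the named source of the problem.

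Nor do the amplitude simulations carry over to filtering. If attention scales S1 and S2 alike, it cancels in S2/S1. Under assumed values (30 patients, log-gain SD 0.3, gain-duration correlation -0.5 to -0.7), the false duration signal was 5% to 6% for the ratio against 45% to 79% for amplitude. Attention could act differently on the two stimuli, and the protocol intends to examine its effect on gating, so the ratio still belongs in the corrected analysis; but no error rate is claimed for it.

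The open-ended confounder list and the unspecified model selection could admit further terms. Neither commits the plan to an interaction. Finally, Aims 2 and 3 mainly concern associations with cough and swallowing, so this point affects interpretation of the SEP results more than the whole of those aims.

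**Conclusion.** The concern holds in this form: as written, the analysis delivers an average attend-ignore difference and does not test whether that difference varies with PD or with its duration. It therefore falls short of the stated purpose of the two runs. This follows from the model terms and needs no simulation. Among the primary peaks, the protocol's own account implicates N2, not P1.

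The percentages show only that the consequence could be material with 30 patients. They rest on assumed slopes, an additive amplitude effect and no covariate adjustment. The 5% rate in the ignore condition holds only because attention was set to zero there. The change should be made before analysis; the point does not undermine the design or the data collection.

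**What to change.** For each SEP amplitude and gating measure, replace the separate condition and duration regressions with a mixed model containing condition, the listed covariates and a participant random effect, fitted in two forms:

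1. **PD and controls:** add group and condition x group. This addresses the question left by the pilot.
2. **PD only:** add disease duration and condition x duration.

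Report the interactions and the condition-specific group and duration effects with confidence intervals, and keep the interactions outside any model selection. Treat an effect that is also present in the ignore condition as better, not conclusive, evidence of altered airway processing, because ignoring may not remove attention fully. The attend-run button press could be summarised as a direct check on attention.

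The cost is SAP wording and one interaction per model, with no new data or visits. The drawback is low power for the interaction with 30 per group, so the SAP should say in advance that a non-significant interaction does not rule attention out.
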